As mentioned above, upon hearing the description of the study, the participant will be required to describe the procedures to the person obtaining consent, summarize what is expected of him or her and list two risks involved. This will ensure that participants understand the implications of their decision to participate and are able to make a well-informed decision and communicate this decision to the person obtaining consent. Consent will be obtained in a private setting by an investigator to minimize any power differential that the participant might feel. Participants unable to communicate with the investigator for any reason will not be included in the study. Only subjects having the capacity to give informed consent will be enrolled in the study. The recruitment process will not be coercive or unduly influencing, as participants enter the research study voluntarily and understand that they have the right to withdraw at any time. Subjects will be told that non-participation in the study will not affect any current treatments they are receiving at VA or elsewhere.

13. Summarize what actually will be done to the subjects during their participation in the study:

The subject will fill out the informed consent. They will then fill out a series of clinician interviews and self-report measures asking questions related to thoughts and feelings about suicide, general mental and physical health, and relationship with other. After these are completed half the group will be randomized to the PLF intervention arm in which Veterans will participate in the 10 weekly groups.

a. Provide a clear description of what is being done for research purposes and what is being done as part of "usual care":

For research purposes: Initial consult with research investigators and consenting, which will take approximately 30 – 45 minutes, completing assessments (1.5 hours) and answering interview-style questions pertaining to the research topic (30 minutes).

Subject matter of the interview includes: communication quality with others, overall life satisfaction, frequency of suicidal ideation or urges, and reasons for attempting suicide.

“Usual care”: Subjects will be able to continue all regular treatment outside of the study.

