b. Provide a detailed **list of tests and procedures** that will be performed for research purposes (e.g., blood tests, urine tests, cultures, interviews, questionnaires, surgical procedures, cardiac catheterization, pulmonary function tests, X-rays, scans, etc) during the course of the study. **List must indicate tests and procedures only for subjects who sign a VA consent form, regardless of where tests and procedures take place:**

Test /Procedure:	Where:	Performed by Whom: (Insert Name or TBD if not yet known)	When:	# of times:
Columbia Suicide Severity Rating Scale (CSSRS)– current & since last visit version	Research office	[name], [name]	0, 3, 6,12, weekly for PLF group participants	4
Access to Lethal Means	Research office	[name], [name]	0, 3, 6,12	4
Beck Depression Scale	Research office	[name], [name]	0, 3, 6,12	4
Beck Hopelessness Scale	Research office	[name], [name]	0, 3, 6,12	4
Self-report log based on the Modified Cornell Services Index (MCSI)	Research office	[name], [name]	0, 3, 6,12	4
Brief Survey of Safety Plan Utilization (BSSPU)	Research office	[name], [name]	0, 3, 6,12	4
Suicide-Related Coping Measure (SRCM)	Research office	[name], [name]	0, 3, 6,12	4
Group Psychotherapy Process Measure*	Research office	[name]	1,5,10 (weeks)	3

PLF treatment arm only		[name]		
Buss-Perry Aggression Questionnaire	Research office	[name], [name]	0, 3, 6,12	4
Reasons for Living	Research office	[name], [name]	0, 3, 6,12	4
Attitudes Towards Seeking Professional Psychological Help	Research office	[name], [name]	0, 3, 6,12	4
Insomnia Severity Index	Research office	[name], [name]	0, 3, 6,12	4
Beck Lethality Scale	Research office	[name], [name]	0, 3, 6,12	4
The Self-Injurious Thoughts and Behaviors Interview	Research office	[name], [name]	0, 3, 6,12	4
Suicide Intent Scale	Research office	[name], [name]	0, 3, 6,12	4
Beck Scale for Suicidal Ideation	Research office	[name], [name]	0, 3, 6,12	4
Barratt Impulsiveness Scale	Research office	[name], [name]	0, 3, 6,12	4

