Interpersonal Needs Questionnaire	Research office	[name], [name]	0, 3, 6,12	4
Mini-International Psychiatric interview (MINI)	Research office	[name], [name]	0	1
McLean Screening	Research office	[name],	0	1

Instrument for BPD		[name]		
PLF Intervention Sessions	Research office	[name]	Weekly	10
Moral Injury Outcome Scale (MIOS)	Research office	[name], [name]	0, 3, 6, 12	4

c. If laboratory tests are part of this protocol, will some or all study-related tests be performed outside this medical center?

YES	NO	N/A	X
-----	----	-----	---

d. Provide a statement that defines who will be financially responsible for the costs associated with participation in the study (e.g., examinations, procedures, drugs, devices, etc.) and a statement that defines what will be provided without cost to the subjects:

The patient will not incur any costs from participating in this study. The PLF intervention will be provided free of charge. In the event of an injury resulting from the research study the facilities of the Bronx VA will be made available to patients.

List all Authorized Prescribers of drugs (whether or not the drug is investigational)

NA

e. VHA Health Record (If yes to (i) below or if clinical resources are to be used, a VHA health record must be created in CPRS [VHA Handbook 1200.05 #29j]).

(i) Will the research intervention possibly lead to physical or psychological adverse events?

YES	X	NO	
-----	---	----	--

(ii) Do you have a process in place to include a copy of the signed informed consent and HIPAA authorization in the medical record for the type research described above for each subject?

YES	X	NO	
-----	---	----	--

If yes, Please describe: **A copy of each consent is scanned into subjects' charts and a hard copy is retained in study records.**

(iii) Did the IRB determine that CPRS flagging is required?

YES	NO	X	
-----	----	---	--

14. Risks:

a. Identify study risk:

No Risk	
Minimal Risk	
Greater Than Minimal Risk	X

b. Describe the steps you could take to minimize risk to subjects, *without changing the science* of the study:

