For investigational drugs, what are the possible risks associated with the study drug relative to possible interactions with medications likely to be used by subjects? **NA**

What will your approach be to such risks? **NA**

Will such subjects be excluded from the study? **NA**

Have you reviewed scientific literature or relevant FDA and Sponsor Advisories alerts or warnings relevant to this medication/device? **NA**

YES		NO	
------------	--	-----------	--

If there was any new information, what were the possible risks to subjects based on this information? **NA**

If there was any new information, how were potential benefits for subjects affected by this information? **NA**

If new information is received from the FDA or Sponsor that may affect the conduct of this study, would you be willing to change the study design or study procedures?

YES		NO	
------------	--	-----------	--

How will you inform subjects of any relevant information from the FDA or Sponsor Advisories? **NA**

What advice will you provide to subjects if there are questions on continuing participation in the study? **NA**

16. Research Safety:

a. Describe your Data Safety Monitoring Plan for subjects (3-4 sentences):

Data Monitoring Committee (through Hines VAMC in Chicago, IL)

b. What information will you be collecting for AEs/SAEs and what is your plan for reporting these to the IRB?

Subjects will be monitored by a study psychiatrist for symptomatic assessment, status of clinical condition and for suicidal ideation. All clinical findings and concerns will be discussed with the PI and adverse events will be reported to the IRB according to institutional guidelines.

This study is likely to have adverse events related to suicide attempts. Safety monitoring for adverse events (AEs) will be conducted in real time by the Principal Investigators and the research coordinators. The PIs will supervise the research and respond directly to patient problems. In the case of AEs, all of them will be indicated on the source documentation for the specific adverse event report form. The PIs will determine the severity of the event, will assign attribution to the event, and will monitor the event until its resolution.

How will you monitor adverse events? Adverse events will be monitored through regular contact with study participants, as well as contact with providers.

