Title: **Group ("Project Life Force") vs. Individual Suicide Safety Planning RCT**

NCT Number: **NCT03653637**

Date: **05/12/2025**

Primary Statistical Analysis Plan

The primary outcome of suicidal behavior will be analyzed using a Cox Proportional Hazard Regression, with treatment condition (PLF+TAU vs. TAU) and baseline suicidal behavior level as predictors, and incidence and time to the first suicidal behavior during the study course as the outcome variables. The model will adjust for treatment site. Kaplan-Meier estimates of the cumulative hazard function for both groups will be graphed and the proportionality assumption checked. If the hazard functions are not proportional, the non-parametric log-rank test will be used instead, with treatment condition as predictor, and we will use a sensitivity analysis to test the effect of baseline suicidal behavior severity by splitting the treatment conditions by the presence/absence suicidal behavior.

Most secondary and other outcomes (depression, hopelessness, thwarted belongingness, aggression dimensions, insomnia and suicide-related coping) will be analyzed in Linear Mixed Effects (LME) regression models. All LMEs will be adjusted for site and will include randomization condition, time, and a randomization by time interaction. The treatment effect of PLF+TAU vs TAU will be the treatment by time interaction. Time will be treated as a linear variable. Mixed-effect models can be fit to data with dropout or missing values as long as the data is missing at random, thus, attrition does not necessarily reduce the number of participants included in these analyses.

For the two outcomes (drug and alcohol use) that are only measured at the one-year follow-up (with retrospective questions about the past 12 months), we will compare between PLF+TAU and TAU with t-tests or Mann-Whitney U tests where appropriate.

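### The CSSRS row does not separate the weekly PLF-only ratings from the outcome ratings by rater, and neither document masks those who rate or classify suicidal behavior

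*Protocol*

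**What the plan says.** Protocol section 13.b has a single row for the "Columbia Suicide Severity Rating Scale (CSSRS)– current & since last visit version". Its timing cell lists 0, 3, 6 and 12 and then "weekly for PLF group participants", its count of occasions is 4, and its staff cell holds two names (removed from the public text) with no division of duties. PLF delivery has a separate row, "PLF Intervention Sessions", with its own staff cell.

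Protocol section 13 states that after the initial assessments "half the group will be randomized to the PLF intervention arm in which Veterans will participate in the 10 weekly groups". Baseline ratings therefore precede randomization.

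The SAP's primary analysis is a Cox model with "incidence and time to the first suicidal behavior during the study course as the outcome variables". It does not say which instrument supplies the events or who decides that an act counts as one. Protocol section 17.b describes the suicidal-behavior outcome as a composite. Neither document mentions blinded or masked assessors, independent assessment, or adjudication of events.

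**The concern.** Participants and group leaders necessarily know the arm in this trial. Masking can therefore protect only the rating of outcomes and the classification of events, and the plan provides it at neither step.

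The weekly CSSRS exists in one arm only, so giving it reveals the arm. If the same person later conducts the 3-, 6- or 12-month interview, that interview is not masked for the PLF participants that person has seen.

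Classifying an act as suicidal behavior under a composite definition takes judgement: was an attempt actual, interrupted or aborted, or was there no attempt? Expectation can move such judgements. A difference between arms on the primary outcome would then be hard to separate from a difference in how acts were scored.

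This point is about who rates and what they know. How often the scale is given in each arm is a separate matter.

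**Working it through.** **Reading the row against the rest of the plan**

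1. Scheduled ratings at 0, 3, 6 and 12 make 4, which matches the row's count. Assuming one weekly rating per session over 10 sessions, the PLF total is up to 4 + 10 = 14, against 4 in TAU. The count of 4 therefore leaves the weekly ratings out.
2. The table can separate staff by task, since PLF sessions have their own row and staff cell. The CSSRS schedules are not separated in this way.
3. The other suicidal-behavior interview at 0/3/6/12, the Self-Injurious Thoughts and Behaviors Interview, also lists two removed names and no masking. Using it as the event source instead would not close the gap.
4. Section 16.c speaks of raters and of clinicians delivering PLF as different roles. That separates delivery from rating but does not mask the rater.

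**Illustration of what unmasked scoring could do**

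The plan gives no figure for this, so there is none to reproduce.

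Inputs from protocol section 17.b: 49% base rate in TAU, N = 145, 20% dropout.

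Assumptions: no true effect; 49% read as a 12-month rate in both arms; exponential hazards; equal allocation; a fraction *m* of PLF events scored as non-events; a factor of 0.9 for 20% dropout spread over follow-up; no allowance for clustering.

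- Apparent HR = ln(1 − 0.49(1 − m)) / ln(0.51)
- Events = 145 × 0.9 × 0.49 × (1 − m/2)
- z = ln(HR) × √events / 2
- Two-sided rejection = Φ(−1.96 − z) + Φ(−1.96 + z)

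| m | HR | Events | z | Rejection |
|---|---|---|---|---|
| 0.05 | 0.930 | 62 | −0.285 | 5.9% |
| 0.10 | 0.864 | 61 | −0.571 | 8.8% |
| 0.20 | 0.739 | 58 | −1.147 | 20.9% |

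For m = 0.10: 0.49 × 0.90 = 0.441; ln(0.559)/ln(0.51) = 0.864; 145 × 0.9 × 0.49 × 0.95 = 60.7; −0.1465 × √60.7 / 2 = −0.571.

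Replacing 0.9 with 0.8, so that dropouts contribute no events, gives 5.8%, 8.4% and 19.1%. A log-rank simulation with 20% exponential dropout (4,000 runs) gave 5.6%, 8.8% and 18.8%, so the formula slightly overstates the 20% case.

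**Opposite direction**

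If raters over-score PLF acts by 10%, set m = −0.10. Then 0.49 × 1.10 = 0.539, HR = ln(0.461)/ln(0.51) = 1.150, events = 67.1, and z = 0.573. Rejection is 8.8%, now mostly against PLF.

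**The case against.** The strongest reply is that the documents show silence on masking, not unmasking by design. Much of that stands, and three stronger readings have to be set aside.

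- **A reader might infer that the same people are shown to do both schedules.** The names are removed and the cell allocates no duties. The two could split the work, and the count of 4 suggests that the cell may describe only the scheduled ratings.
- **A reader might infer that the raters know every participant's arm.** Baseline ratings precede randomization. Working out TAU membership by elimination requires one rater to see every PLF participant. The row comes from one site's application, while section 4 gives 180 subjects at this site and 320 in total.
- **A reader might infer that the investigators' adverse-event role decides the endpoint.** Section 16.b says "The PIs will determine the severity of the event, will assign attribution to the event", but that concerns safety reporting. No text says that it determines whether an act counts in the Cox model.

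It is also fair to say that the SAP does not name the CSSRS as the event source, that the misclassification rates have no source in the documents, and that re-rostering may come late. Monitoring reports date from 2018/2019 and the SAP from 05/12/2025.

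None of this supplies masking. If the raters do split duties, or if a masked classifier exists, the plan needs to say so. Late timing weakens the case for re-rostering but not for masked classification before analysis.

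**Conclusion.** The point holds in a limited form. The protocol lists a PLF-only weekly rating and the outcome ratings against one undivided pair of raters. Nothing in either document masks post-randomization raters or the classifiers of suicidal behavior. The natural reading exposes at least some outcome raters to knowledge of PLF membership, and the primary endpoint depends on judgement.

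The size is not established. The illustrated hazard ratios of 0.93 to 0.74, and rejection rates of about 6% to 21%, depend wholly on assumed one-sided misclassification of 5% to 20%. Equal over-scoring in PLF would push the other way. They show that modest mis-scoring could matter with about 60 events, not that it has occurred. No sample-size or power figure changes.

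This should be corrected. Confidence is medium, because rater identity and the source of endpoint events are not stated.

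**What to change.** 1. **Split the CSSRS row.** Give the weekly PLF ratings their own row and staff cell. Where listed staffing allows, assign the 3/6/12 interview outcomes to a listed rater with no PLF sessions, weekly ratings or group-process measures. Add a script line asking participants not to disclose their group, and log any unmasking. Place instruments whose content may reveal the arm, such as the services log and the safety-plan survey, after the suicidal-behavior interviews.
2. **Classify events masked, before analysis.** Have an existing investigator with no PLF delivery or rating role classify each candidate event from a narrative with arm and group references removed. State in the SAP that the primary Cox model uses this classification. This remains possible even if data collection is complete.
3. **Report it.** If earlier ratings were made unmasked, say so in the trial report.

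The cost is redaction work, less rota flexibility and some residual unmasking through what participants say. No added visits are needed. Whether a listed rater is free of PLF duties cannot be checked from the public text. If none is, step 2 carries most of the protection, although it cannot undo what an unmasked interviewer failed to elicit or record.

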All data will be de-identified before it is entered into a redcap database at the JJPVA, Philadelphia VA, Northport VA, and Central Texas VA over the intranet. All principal analyses will be conducted based on the intention-to-treat principle. Linear mixed models will be used to examine changes in primary and secondary outcomes for Veterans over time and to examine whether the effects of PLF and TAU on these outcomes vary with time adjusted for the time-dependent treatment, covariates of interest and imbalanced baseline prognostic factors, using data reduction methods as appropriate. *For the PLF subjects, individual's random effect will be nested within the group they are assigned to, while for TAU subjects, they will be nested within the clinician effect.* All data will be entered into an SPSS database at the JJPVA constructed by the data manager. Tenets of our data system include double data entry, range checks and exclusion of identifiers that can be directly traced to individuals. Preliminary analyses will include computing descriptive statistics and inspecting features and patterns of data to determine whether data transformations are needed. Quantitative measures will be graphed and their distribution inspected for any outlier value, which will be winsorized. All principal analyses will be conducted based on the intent-to-treat principle, that is, all Veterans with data will be included, regardless of the actual treatment received. For subjects who drop out during the study, their data up to that point will be used, but not carried forward to subsequent time points. We will also conduct an economic cost analysis of the Project Life Force intervention to compare cost effectiveness of telehealth groups versus the in-person groups pre-COVID. We will use an implementation science framework, The Consolidated Framework for Implementation Research, to determine barriers and facilitators of the telehealth-delivered PLF safety planning intervention. Development of the script and qualitative analysis will be conducted by [name]; a qualitative and implementation expert.

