Analyses to Determine Generalizability of Results: We will compare the baseline characteristics (e.g., age, sex, education) of the study population to those that declined participation, and will evaluate reasons for refusal that will be tracked. A sensitivity analysis using the propensity score methodology would be applied if those who refuse participation were significantly different on important measures from the participants. Missing data and loss to follow-up are usually concerns in longitudinal studies presenting problems in interpretation. The validity of the resulting inferences depends critically on the underlying mechanism that generates the missing observation- MAR, MCAR or MNAR.⁴⁴ Both survival analysis and mixed-effect models, the proposed

statistical methodology, can handle data that is missing at random or missing completely at random; that is, if the mechanism for missing data does not depend on the value of the response variable, given the information in the predictor variables already in the model (treatment condition and baseline scores), then no further adjustment is necessary.

However, when missing data are related to outcomes of interest even after conditioning on the known data (i.e. treatment condition), such as when in some patients side-effects of the active treatment affect the suicidal behavior risk and also cause drop-out, parameter estimates and resulting

tests of hypotheses will be biased, and this can affect the generalizability as well as the reproducibility of the results. To address this problem, we will look for patterns of missingness. For example, data will be stratified according to their missing pattern (e.g., early and late termination, and incomplete follow-up); and, assuming a monotonic missingness pattern applies, we will use Diggle methodology, allowing us to examine the effects of missing-data patterns on outcome measures. We will explore other patterns using the techniques referenced above.

b. Provide power analysis or describe how sample size was determined:

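### Mixed-model covariates: the protocol's set depends on chance imbalance and an undefined treatment term, the SAP's is fixed but does not use baseline for precision, and neither document says which governs

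*Protocol*

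**What the plan says.** Three places describe what goes into the mixed models.

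- Protocol, item 17.a, first paragraph. The scope is wide: "Linear mixed models will be used to examine changes in primary and secondary outcomes for Veterans over time". The models are "adjusted for the time-dependent treatment, covariates of interest and imbalanced baseline prognostic factors, using data reduction methods as appropriate". The same paragraph commits to intention to treat: "all Veterans with data will be included, regardless of the actual treatment received".
- Protocol, item 17.a, text on generalizability and missing data. Missing data are said to need no further adjustment if missingness does not depend on the response, "given the information in the predictor variables already in the model (treatment condition and baseline scores"). This places baseline scores in the model regardless of imbalance, and does not mention site.
- SAP, second paragraph. "All LMEs will be adjusted for site and will include randomization condition, time, and a randomization by time interaction". Time is linear, and "The treatment effect of PLF+TAU vs TAU will be the treatment by time interaction". No baseline covariate, imbalance rule, data reduction or time-dependent treatment term appears.

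The SAP's primary analysis is separate. It is a Cox regression "with treatment condition (PLF+TAU vs. TAU) and baseline suicidal behavior level as predictors", and "The model will adjust for treatment site".

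The protocol is dated 08/03/2024 and the SAP 05/12/2025. Neither states that the SAP replaces item 17.a.

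**The concern.** There are three separate problems.

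**Selection on imbalance.** In a randomised trial, baseline differences between arms arise by chance. A rule that admits covariates because they look imbalanced makes the fitted model depend on that chance and on an analyst's undeclared threshold. The choice is made after data from both arms have been seen.

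**The time-dependent treatment term.** If this is treatment actually received, or concurrent care, it is a post-randomisation variable. Adjusting for it would no longer estimate the effect of assignment. The protocol allows usual treatment to continue (item 13.a) and records service use at 0, 3, 6 and 12 (item 13.b), so such a variable will exist.

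**Use of baseline.** The SAP's set is fixed, which is the right direction. But with a free arm main effect at time 0, the model spends information estimating a baseline arm difference that randomisation sets to zero in expectation. The treatment-by-time estimate is then less precise than the same data allow.

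At stake are the credibility and precision of the secondary comparisons.

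**Working it through.** No figure in the plan depends on this point, so there is none to reproduce. The first step compares the texts. The others are illustrations, with their assumptions stated.

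**1. The texts side by side**

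| Term | Protocol 17.a, models | Protocol 17.a, missing data | SAP mixed models |
|---|---|---|---|
| Site | not named | not named | yes |
| Baseline scores | only as unnamed covariates of interest, or if imbalanced | yes | not named |
| Imbalanced factors | yes, no rule | no | no |
| Time-dependent treatment | yes, undefined | no | no |
| Treatment by time | implied | not stated | yes |

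The three descriptions differ, and nothing ranks them.

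**2. How often chance would change the covariate set.** Assume K independent candidates, each called imbalanced at p < 0.05. Neither K nor the threshold is in the documents. P(at least one) = 1 − 0.95^K, which is 22.6% for K = 5 and 40.1% for K = 10. Correlated candidates would lower these figures.

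**3. Type I error.** This was simulated under the null with N = 145 (protocol item 17.b), 1:1 allocation, one follow-up, K = 5 or 10, covariate R² of 0.3 or 0.5, two-sided 5% and 6,000 runs per setting.

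- Fixed covariates: 4.8% to 5.3%.
- Imbalance-selected covariates: 3.7% to 4.3%, slightly conservative.
- Best of unadjusted, fixed and imbalance-selected: 7.9% to 8.9%.

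The selection rule does not inflate the error. Freedom to pick among models would.

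**4. Adjusting for treatment received.** In least squares, the adjusted arm coefficient equals the unadjusted coefficient minus δγ. Here δ is the arm difference in the treatment variable and γ is that variable's coefficient in the adjusted model. Take a true arm effect of 0 and an assumed γ of 0.24 outcome SD per unit:

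- δ = 0: bias 0
- δ = 0.5: −0.5 × 0.24 = −0.12 SD
- δ = 1.0: −1.0 × 0.24 = −0.24 SD

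A simulation gave the same values to two decimals. The sign and size depend on assumptions. There is no bias when assignment does not shift the variable.

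**5. Precision from a common baseline mean.** The visits are 0, 3, 6 and 12 (protocol item 13.b), so n = 4, Σt = 21 and Σt² = 189. Assume equal arms, complete data and a random intercept with within-person correlation ρ, and let c = ρ/(1 + 3ρ). Up to a constant, the information on the arm differences in intercept and slope is:

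- I_ii = 4 − 16c
- I_is = 21 − 84c
- I_ss = 189 − 441c

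Setting the intercept difference to zero reduces the slope-difference variance by the fraction I_is²/(I_ii × I_ss) = 7(1 − ρ)/(12 + 8ρ):

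- ρ = 0.3: 4.9/14.4 = 34%
- ρ = 0.5: 3.5/16 = 22%
- ρ = 0.7: 2.1/17.6 = 12%

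The time unit cancels.

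**6. Two routes that do not give this gain.** Adding only the main effect of a baseline covariate removes between-person variance. The slope difference depends on within-person variance, so its precision is unchanged (simulated variance ratio 1.000). Modelling only visits 3, 6 and 12 while keeping the slope as the effect is worse. The time sum of squares falls from 189 − 21²/4 = 78.75 to 189 − 21²/3 = 42, so the slope variance rises by 78.75/42 = 1.875 times.

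**The case against.** The strongest reply is that the SAP settles the matter. It is later, specific and fixed, and an analyst would naturally follow it. That largely stands: this is a missing governing statement more than two equal rival plans. It is not fully closed, because the SAP lists outcomes for most, not all, of the secondary and other measures. Suicidal ideation, the outcome named in the protocol's statement of purpose, is not in that list. The SAP's reference to all mixed models can be read to cover it, but does not name it.

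Four stronger readings are tempting and not supported.

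- *The protocol breaches intention to treat.* The term is undefined. Treatment received is the more natural reading, since the sentence already covers effects varying with time. But it may be loose wording for treatment by time, which the SAP includes and which raises no conflict.
- *Imbalance selection inflates false positives.* Step 3 shows it does not. The 7.9% to 8.9% needs an analyst to report the best of three models, which neither document proposes.
- *Strong predictors that balance are left out.* Covariates of interest are a separate route into the protocol's model, and the missing-data text puts baseline scores in it.
- *The primary result is at risk.* The protocol's scope sentence does mention primary outcomes, but the SAP's Cox model has its covariates fixed, including baseline suicidal behavior and site.

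Nor should every baseline instrument be counted as an independent 5% test: the plan specifies no such tests, and these scales are likely correlated. The familiar single-visit gain from a correlated covariate does not carry over to a slope interaction (step 6).

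**Conclusion.** The point holds as a modest one about the mixed models. The documents give three covariate descriptions without ranking them; one depends on chance imbalance and contains an undefined treatment term. No intention-to-treat breach, error inflation from the selection rule itself or defect in the SAP's primary Cox model is established.

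The measurable benefit is precision: about 12% to 34% lower variance for the treatment-by-time estimate, for assumed within-person correlations from 0.7 down to 0.3. It rests on linear trajectories, a random intercept, equal arms and complete data. Random slopes, dropout or the nesting by group and clinician planned in the protocol would change it. If trajectories are not linear, the fitted intercept is not the baseline mean, and the constraint should then be placed on the time-0 mean itself.

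**What to change.** Change the wording in both documents:

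1. State that the SAP's prespecified terms govern every mixed model, and name all the outcomes covered, including suicidal ideation if it is to be analysed this way.
2. Delete selection by imbalance, or keep it as a labelled sensitivity analysis with a candidate list and a rule.
3. Remove time-dependent treatment from the main models, or define it as treatment by time.
4. Keep baseline as a response and constrain the arms to a common baseline mean; with linear time this means omitting the arm main effect at time 0. Alternatively, model follow-up visits only with baseline as a covariate, but then redefine the effect as an arm difference at follow-up, for the reason in step 6. Do not enter baseline as both response and covariate.
5. Align the protocol's missing-data text with the chosen terms.

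The cost is a short amendment, ideally before the outcome data are examined by arm. No new data are needed.
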